5-24-2021

Pharmacologically-based Strategies for Opioid Substitution Therapy During Pregnancy

PRO18070495 / STUDY19100128

NCT03831113

Protocol version 1.8

The Eunice Kennedy Shriver National Institute of Child Health and Human Development (NICHD)

Principal Investigator:

[name]
Magee-Womens Hospital
[name]
[name]

Specific Aim 4

Specific Aim 4 compares dose reduction strategies for Suboxone or Subutex in pregnancy that are based on the pharmacodynamic and pharmacokinetic characteristics of BUP.

a) Primary Research Questions

1. Is adherence during dose reduction influenced by the magnitude or frequency of a given dose reduction?
2. Is adherence during dose reduction influenced by dosing frequency?
3. Does mu receptor sensitivity change during dose reduction?

b) Eligibility Criteria

Inclusion Criteria – must meet all of the following:

1. On a stable BID, TID or QID dosing regimen of BUP for at least 2 weeks as part of an established medication- assisted treatment (MAT) program.
2. Willingness to undergo supervised dose reduction
3. Subjects on BID, TID or QID dosing, willing to be assigned to the Magnitude, Frequency, or Dosing group, depending on their current dosing
4. Single gestation between 14-30 weeks at the initiation of dose reduction
5. On a BUP dose between 6- 24 mg daily (lower doses will not provide sufficient data points)
6. Willingness to have urine samples tested for drugs of abuse and blood samples tested for BUP+M concentrations during the Medical Supervised Withdrawal (MSW) clinic appointments
7. Willingness to attend weekly or biweekly MSW clinic appointments and to have daily contact via text messaging to complete daily logs of sleep quality, withdrawal symptoms and symptoms of craving. Subjects may consent to receiving daily text messages with a link to a REDCap where they can complete the daily questionnaires electronically. Alternatively, they may complete hard copies of the questionnaires and return them during their weekly clinic visits.
8. Willingness to attend psychosocial support meetings, as needed.

Exclusion criteria – cannot meet any of the following:

1. Current use of cocaine, heroin, benzodiazepines, barbiturates, phencyclidine (PCP), or opioids other than BUP
2. Currently taking more than two mental health medications

3. Active moderately severe depression (PHQ-9 score ≥ 15 or suicidal ideation)
4. Current incarceration

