5. Lack of a phone or transportation to and from clinic.
6. Major fetal malformation
7. Mother with significant vaginal bleeding or serious medical or obstetrical complication that could adversely affect study
8. Planned delivery at another institution
9. HIV or AIDS
10. Diagnosis of schizoaffective disorder or psychosis

c) Pre-Study Screening

The following information will be obtained for consented patients 1-2 weeks prior to initiation of the dose reduction:

1. Demographic information: age, race, weight, height
2. Medical history: medical disorders, mental health disorders
3. Obstetrical history, including the outcome of all prior pregnancies
4. Social history: alcohol, tobacco, and illicit drug use
5. Depression Screening (Patient Health Questionnaire-2 (PHQ-2) and Patient Health Questionnaire-9 (PHQ-9), if necessary)
6. Intake questionnaire
7. Concomitant medications – Subjects who use withdrawal mitigating agents such as Benadryl or clonidine will not be excluded from the study. Research staff will track the use of all concomitant medications.
8. Project gestational age and estimated date of delivery
9. Vital signs: blood pressure, heart rate, respiratory rate
10. Maternal blood work: BUN, creatinine, albumin, total protein, ALT, AST, BUP + M concentrations, maternal DNA for drug metabolizing enzymes, and PBMC analysis (Pitt site only), (the first sample for PBMC analysis may be drawn at any time during pregnancy)
11. Urine sample will be collected and tested for the presence of drugs of abuse.
12. Obtain routine medical record release forms and review procedures for the upcoming study visit.

Notes:

- *BUN, creatinine, albumin, total protein, ALT, and AST will not be performed if results are available in the subject's medical record as part of the standard of care during this pregnancy or if testing was performed during a previous Pre-Study Screening.*

d) Study Design

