The pharmacologic properties of BUP that inform this specific aim include a long half-life that suggests that any dose reduction should not occur more often than every 5 days to allow the impact of that dose change to manifest. The long half-life also suggests that a higher reduction (i.e. 2 mg) will be well tolerated as the reduction in drug exposure (i.e. the reduction in plasma concentrations over time) will be gradual over the ensuing 5 days till a new steady state is reached. The third PK and PD characteristic of BUP is that plasma concentrations are better sustained above a specified critical value with more frequent dosing.⁵¹ Based on these pharmacologic characteristics of BUP, we will evaluate three strategies for supervised dose reduction. We will recruit 3 groups of pregnant women who are on a stable dose of BUP and are committed to supervised dose reduction. Recruitment will occur in our Pregnancy Recovery Center (PRC), from offices of other BUP writers, and from the Emergency Department (ED) at Magee. We will also enlist [name], MD at High Risk Obstetrical Consultants, in Knoxville, TN to assist in recruitment of eligible subjects at his institution for Specific Aim 4 only, pending IRB approval. [name] is an expert in dose reduction/detoxification during pregnancy and has published extensively on this topic. [name] will adhere to this multicenter protocol and Data Safety Monitoring Plan and report periodically to [name].

At MWH, pregnant women with an opioid use disorder generally come for initiation of methadone or BUP as part of a MAT program. They often present to the ED and are told to contact the PRC if they wish to start BUP or they are admitted if experiencing withdrawal for transition to methadone. Those who prefer to initiate treatment with Suboxone or Subutex will be targeted for recruitment. [name] is a primary provider at High Risk Obstetrical Consultants for opioid dependent women and we structured our dose reduction strategy based on his experiences.

Consenting subjects will be assessed for depression at the Pre-Study Screening. The Patient Health Questionnaire-2 (PHQ-2) will be administered as a screen for depression. If the PHQ-2 score is 3 or greater, major depressive disorder is likely and subjects will be further evaluated with the Patient Health Questionnaire-9 (PHQ-9). The PHQ-9 is a multipurpose instrument for screening, diagnosing, monitoring and measuring the severity of depression.

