- A PHQ-9 score of ≥ 15 represents moderately severe depression. Subjects with a score of ≥ 15 at the Pre-Study Screening will be excluded from participating in the study and will be referred to a mental health provider.

Note: Question 9 on the PHQ-9 is a single screening question on suicide risk. If a subject answers yes to question 9, they are ineligible to continue with the study and will be immediately referred to a mental health provider for further assessment.

Once recruited subjects are on a stable dose of Suboxone or Subutex for 2 or more weeks, we will initiate one of three dose reduction strategies. We will compare tolerance in the same person to an alternating 1 mg vs 2 mg weekly reduction (Magnitude group, n=10). In a second group (Frequency group, n=10) we will compare tolerance in the same person to an alternating 2 mg reduction occurring weekly vs bi-weekly. All subjects in the Magnitude and Frequency groups will be on TID or QID dosing. In a third group (Dosing Group, n=10) we will compare tolerance to either the Magnitude or Frequency reduction schedule in women who are on a BID dosing regimen. The comparisons in these three groups will address those fundamental questions required for development of a rational dose reduction strategy. Each of these strategies addresses a specific question about maternal accommodation to the specified dose change. The dose reduction magnitude of 1 mg vs 2 mg and the frequency of reduction of weekly vs bi-weekly selected are based in large part on the work of Sigmon et al.⁴⁷ but larger and more frequent reductions could be considered. We chose this modest reduction strategy as we were concerned that more aggressive changes could lead to subject withdrawal and dissatisfaction. In the study of Sigmon et al.⁴⁷, only 50% of participants were opioid abstinent with the 4-week taper (i.e. 1.75 mg per week). We believe a slower taper regimen could improve upon this outcome. Table 1 provides an example of the dose reduction strategy assuming, as an example, a starting dose of 16 mg daily. Subjects on TID or QID dosing will be assigned to either the Frequency or Magnitude groups based on their current dosing. Subjects on BID dosing will be assigned to the Dosing group.

- Subjects assigned to the Frequency group will have dose reductions of 2 mg on alternating intervals of 1 and 2 weeks.
- Subjects assigned to the Magnitude group will have alternating reductions of 1 then 2 mg every week.

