In all 3 groups, daily adherence, cravings and sleep measures will be compared within and across groups. During the Pre-Study Screening, we will explain the study to the subject and ask that she completes an Intake Questionnaire to better understand any previous experiences she may have had with opioid treatment or detox programs. We will also perform urine and blood testing to assure all entry criteria are fulfilled. Once consent is obtained, we will initiate a Suboxone or Subutex dose reduction schedule similar to the one shown in Table 1. To ascertain the impact of a dose change, all subjects will complete 4 daily VAS questionnaires similar to those used by Dunn et al. ⁴⁶ to assess withdrawal, cravings, sleep duration and sleep quality. The scales will range from a score of 0-10 for each question. Subjects that wish to be contacted via text will be sent a daily text with a link to the REDCap website where they can complete the VAS

questionnaire electronically throughout the dose reduction process. Subjects that are unable to receive daily text messages will be provided hard copies of the VAS questionnaire and instructed to return the completed forms to research staff at their next appointment. Clinic visits will occur weekly or biweekly at which time we will monitor plasma BUP+M, neurotransmitter and cotinine concentrations and perform a comprehensive urinary toxicology test. Additionally, at each clinic visit we will administer the Weekly Follow-up and Weekly Smoking and Alcohol Use questionnaires. We will also collect any completed VAS forms, if applicable, and perform COWS and Subjective Opioid Withdrawal Scale (SOWS) scores to assess current clinical and subjective symptoms of withdrawal and satiety. All subjects will receive psychosocial support, as needed. The timing of the subject's scheduled visits will be determined by their healthcare provider.

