concentration each week to the subjects VAS scores on craving and withdrawal symptoms. In women who supplement their weekly BUP regimen with other opioids detected at the weekly clinic visits their VAS questionnaires on withdrawal and craving will be scored as 100. Assay Methods: BUP+M will be assayed using UPLC-MS-MS. We have developed and validated this assay and with the new TQS system the LOQ is 15 ng/ml in plasma. BUP in hair and other tissues will be measured by modification of this method and incorporating elements of methods reported in the literature ^{30,31,33}. Cotinine will be measured by minor modification of the published method ⁵⁵.

Anticipated sum of mean VAS scores	Percent Reduction in VAS scores	Sample Size
120	0.15	25
120	0.20	15
120	0.25	10
120	0.30	7

D. Study Procedures

D.1 Screening for Eligibility

The inclusion/exclusion criteria will be reviewed with the patient's chart. Any woman who appears to be eligible will be informed about the study. If a patient appears to meet the criteria for enrollment and expresses interest in the study, she will be told about the study and asked to sign the informed consent form. She will be asked to sign a medical records

release so that the medical records may be obtained. A copy of the signed consent form will be provided to the patient.

D.1.i. Gestational Age Determination

We will use the criteria recommended by the American Congress of Obstetricians and Gynecologists (ACOG).

D.2 Informed Consent Procedures and Documentation

Written informed consent will be obtained before entry into the trial. Full disclosure of the nature and potential risks of participating in the trial will be made. Women who are not fluent in English will be enrolled by a person fluent in their language and both verbal and written informed consent obtained in that language; if such are not available, they will not be included.

D.3 Specimen Collection

Per standard research procedures for Labor and Delivery samples, Magee Womens Hospital employs staff as part of the Obstetric Specimen Procurement Unit (OSPU), which is responsible for the collection of research study samples on the Labor and Delivery unit. Labor and Delivery samples will only be collected if possible. There is a 3-day window for collection of hair samples. Maternal and infant samples will be collected as shown in Table 2.

D.4 Specimen Analysis and Collection of Negative Control Samples

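### Suicidal ideation is an exclusion, but women scoring 0–2 on the PHQ-2 are not scheduled for any direct question about it before the taper starts

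*Combined protocol and SAP*

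**What the plan says.** Exclusion 3 in section b) Eligibility Criteria reads "Active moderately severe depression (PHQ-9 score ≥ 15 or suicidal ideation"). Section c) Pre-Study Screening lists, for the one to two weeks before dose reduction, "Depression Screening (Patient Health Questionnaire-2 (PHQ-2) and Patient Health Questionnaire-9 (PHQ-9), if necessary"). Section d) Study Design gives the sequence. Every consenting woman gets the PHQ-2 as a depression screen, and then: "If the PHQ-2 score is 3 or greater, major depressive disorder is likely and subjects will be further evaluated" with the PHQ-9. A PHQ-9 total of 15 or more excludes.

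A note in the same section adds: "Question 9 on the PHQ-9 is a single screening question on suicide risk". A positive answer to that item makes the woman ineligible and leads to immediate referral to a mental health provider.

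**The concern.** Two criteria share one screening path. The depression criterion depends on a score, so a short screen followed by a longer one suits it. The ideation criterion does not depend on a score: a positive item 9 excludes whatever the PHQ-9 total. Yet item 9 is reached only through the depression score. A woman with ideation and a PHQ-2 of 0–2 is not scheduled to be asked.

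What is at stake is safety rather than inference. The sponsor has decided that women with ideation should not undergo this taper and should be referred at once. The subjects are pregnant women with opioid use disorder, and the protocol itself expects some to have withdrawal symptoms, to be intolerant of reductions and to be at risk of relapse. Under the stated sequence, that protection reaches only those who score 3 or more on the PHQ-2, or whose ideation comes to light in some other way.

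**Working it through.** The protocol states no figure on this point, so the check is mainly a reading of the screening path.

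**Step 1. Is ideation sufficient for exclusion?** Yes. Exclusion 3 joins the PHQ-9 threshold and ideation with *or*, and the note in section d) makes a positive item 9 disqualifying with no reference to the total.

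**Step 2. Where is ideation asked about?** Only in PHQ-9 item 9. No other suicide-risk question is named.

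**Step 3. Who gets the PHQ-9?** Section c) says "Patient Health Questionnaire-9 (PHQ-9), if necessary". Section d) supplies the only stated trigger, a PHQ-2 score of 3 or more. Scores of 0, 1 and 2 do not reach it.

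**Step 4. Could another step before the taper catch it?**

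| Step | What the protocol says of it | Described as asking about current ideation? |
|---|---|---|
| Chart review (D.1) | "The inclusion/exclusion criteria will be reviewed with the" patient's chart | No; finds only charted ideation |
| Medical history (section c) | Records mental health disorders | No |
| Intake Questionnaire (section d) | "Intake Questionnaire to better understand any previous experiences she may have had with opioid treatment or detox programs" | No; items not reproduced |

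**Step 5. Could a later step catch it?** Section d) says "at each clinic visit we will administer the Weekly Follow-up and Weekly Smoking and Alcohol Use questionnaires", together with the COWS and SOWS and the daily scales for withdrawal, craving and sleep. None is described as covering mood or suicide risk, although the Weekly Follow-up items are not reproduced. The Aim 4 removal criteria in section G concern positive drug screens and unreturned drug, not ideation.

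**Step 6. Scale, by assumption.** Let *p* be the share of otherwise eligible women who have a PHQ-2 of 0–2 and ideation that is neither charted nor volunteered. The documents give no value for *p*, so the values below are assumed. The planned number is 3 groups × 10 = 30. Treating women as independent:

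- Chance of at least one such woman = 1 − (1 − *p*)^30
- Expected number = 30 × *p*

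| Assumed *p* | Chance of at least one in 30 | Expected number |
|---|---|---|
| 0.5% | 1 − 0.995^30 = 0.140 | 0.15 |
| 1% | 1 − 0.99^30 = 0.260 | 0.3 |
| 2% | 1 − 0.98^30 = 0.455 | 0.6 |
| 5% | 1 − 0.95^30 = 0.785 | 1.5 |

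These figures count women enrolled despite the exclusion, not harm. The conclusion does not depend on them.

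**The case against.** The strongest reply is that this is a deliberate two-step screen. Ideation appears inside the parenthesis that defines active moderately severe depression, so it can be read as one marker of that condition rather than a criterion to be checked in everyone. On that reading, reaching item 9 only at the second step is coherent. This is a possible reading of exclusion 3 taken alone. It fits poorly with the note in section d), which makes item 9 disqualifying by itself, whatever the depression score.

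A second reply is that the wording about necessity is permissive. Staff who see a psychiatric diagnosis or medication could give the PHQ-9 to a woman scoring 0–2. They could, but the protocol does not tell them to, and the only content it gives that wording is the PHQ-2 threshold.

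Third, several relevant materials are not in the file: the Intake and Weekly Follow-up items, the PHQ-2 items and the Data Safety Monitoring Plan. The existing surveillance approach is mentioned but not described. A suicidality question somewhere among these cannot be ruled out, and that limit stands. The claim is therefore only that none is specified. Anything found after enrolment would also come too late for an exclusion meant to act before the taper.

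Fourth, the women are already in treatment. They have daily symptom logs, weekly or biweekly visits and counseling as needed, and they may return to the last tolerated dose. This does lower the likely consequence, and it is a reason to keep the point in proportion. It does not replace asking the question.

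Finally, the probabilities rest wholly on assumed shares. That is correct, and they should carry no weight beyond illustration.

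**Conclusion.** The concern holds. As written, the protocol makes suicidal ideation an exclusion but specifies no direct question about it for women scoring 0–2 on the PHQ-2. Following the stated sequence can therefore enrol a woman whom the protocol means to exclude and refer.

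The gap is confined to ideation that is neither charted nor volunteered, and to the ideation part of exclusion 3. Its size cannot be estimated from the documents; the range of 14% to 79% for at least one such woman among 30 follows from assumed shares of 0.5% to 5%. The conclusion assumes that the questionnaires not reproduced contain no suicidality item given to every woman before the taper. No endpoint, comparison or sample size is affected. It is a narrow safety point that should be corrected because the correction is cheap.

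**What to change.** Amend the depression-screening item in section c) and the matching text in section d) so that every consented woman answers PHQ-9 item 9, or completes the full PHQ-9, at Pre-Study Screening regardless of her PHQ-2 score. Leave the present consequence unchanged: a positive answer means ineligibility and immediate referral to a mental health provider. If an existing intake form already asks every woman about current ideation, naming that item in section c) and tying it to the same rule would serve equally well.

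The cost is a short amendment using an instrument and a referral path already in the protocol, a few minutes per woman at one visit, and possibly a few more exclusions and referrals. The planned 30 subjects and the analysis stay as they are.

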Week 1	16	16	Refer to the appropriate dose schedule in the Frequency or Magnitude columns
Week 2	14	15	
Week 3	14	13	
Week 4	12	12	
Week 5	10	10	
Week 6	10	9	
Week 7	8	7	
Week 8	6	6	
Week 9	6	4	
Week 10	4	3	
Week 11	2	1	
Week 12	2	0	
Week 13	0	0	

e) Statistics

The outcome(s) of interest are the pharmacodynamic endpoints that reflect the acclimatization of the mu receptors and opioid-affected brain functions. Each subject in a group will undergo alternating treatments to minimize any between subject differences that would impact the response to the decrease in dose. In this study, we will rely on scores from the self-administered VAS questionnaires. We will determine both an average and highest value for each of the VAS questionnaires weekly. The average values over the 7 days of

that given dose from the VAS questionnaires will be combined to create a single score for each week. A similar approach will be taken for the highest rather than average values. Based on the study of Dunn et al ^{46,47}, the mean value for the withdrawal VAS questionnaire (scale 1-10) in non-pregnant subjects was 30 with a standard deviation of ~25. These values are estimates since graphs were provided but not tabular data. A difference of 25% in the VAS combined scores between any of the comparisons would seem clinically meaningful. Thus, a sample size of 10 in each group is sufficient to detect a difference in VAS scores between any of the comparison groups. The comparisons in the Frequency group will be VAS scores between the 1 vs 2 week reductions. The comparisons in the Magnitude group would be VAS scores between the 1 and 2 mg reductions. The comparison in the Dose group will be a comparison of the VAS scores during the 1 mg and 2 mg reductions. Also, VAS scores in the Dose group will be compared to the VAS scores in the Magnitude group both at the 1 and 2 mg reductions. The change in mu receptor sensitivity will be determined by comparing the BUP+M

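### The rule that splits TID/QID women between the Magnitude and Frequency groups cannot determine the group, so the across-group comparisons are open to confounding

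*Combined protocol and SAP*

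**What the plan says.** **Allocation.** Section d plans three groups of 10. BID women go to the Dosing group. For the rest, "Subjects on TID or QID dosing will be assigned to either the Frequency or Magnitude groups based on their current dosing". The same section states: "All subjects in the Magnitude and Frequency groups will be on TID or QID dosing". Table 1 agrees, showing both regimens under Frequency and under Magnitude. Inclusion criterion 3 (section b) requires women to be "willing to be assigned to the Magnitude, Frequency, or Dosing group, depending on their current dosing". Nothing in the document links TID or QID to a particular group, and no randomisation, alternation or other allocation method is described.

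**Comparisons.** Section d announces: "In all 3 groups, daily adherence, cravings and sleep measures will be compared within and across groups". Section e (Statistics) lists the within-group contrasts and one between groups: "VAS scores in the Dose group will be compared to the VAS scores in the Magnitude group", at both the 1 mg and the 2 mg reductions. The control offered for differences between women is the alternating design: "Each subject in a group will undergo alternating treatments to minimize any between subject differences". No adjustment for regimen, starting dose or site is described.

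**The concern.** An allocation rule must produce a group from what is known about the woman. Here the stated criterion, current dosing, takes the same values in both groups. It separates BID women from the others and then stops. The 20 women in Magnitude and Frequency are divided by an unstated, non-random route.

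This matters only where groups are set against each other. Two such uses are planned: the general across-group comparison in section d, and Dosing vs Magnitude in section e. The second is the only listed comparison between dosing frequencies, so it is the one that bears on primary question 2. The protocol also gives a reason to expect regimen to be prognostic, since it holds that "plasma concentrations are better sustained above a specified critical value with more frequent dosing". If the TID/QID mix, starting dose or site differs between groups, a difference in VAS scores cannot be credited to the reduction strategy. The Magnitude group may then also be an unrepresentative sample of TID/QID women against whom to judge BID dosing.

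**Working it through.** **Step 1: does the rule determine a group?** Set the statements side by side.

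| Current regimen | Groups open to it (section d, Table 1) |
|---|---|
| BID | Dosing |
| TID | Magnitude or Frequency |
| QID | Magnitude or Frequency |

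Only the first row has a single answer.

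**Step 2: is the sizing consistent with between-group use?** Inputs from section e are SD about 25, a combined score of 120, and differences of 15, 20, 25 and 30% (18, 24, 30 and 36 points). Alpha, sidedness and power are not stated. A two-independent-group t-test with SD 25, one-sided alpha 0.05 and 80% power (my assumptions) gives 25, 15, 10 and 7 per group, matching all four rows of the sample-size table. A paired two-sided t-test with SD of differences 25 gives 18, 11, 8 and 6 at 80% power and 23, 14, 10 and 8 at 90%, neither of which matches. Other pairings of SD and error rates also reproduce the table with the two-group test (for example SD 22, two-sided, 80% power). The match shows consistency with a between-group test. It does not prove that one was intended. No stated figure depends on the allocation rule, so none needs correcting.

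**Step 3: how large could the bias be?** The documents give no TID-vs-QID effect, so let it be g points on the combined score and try g = 10, 20 and 30. If the shares of QID women in the two groups are p1 and p2, the bias in Magnitude vs Frequency is g × (p1 − p2).

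- One regimen per group: bias = g × (1 − 0) = 10, 20 or 30 points.
- 70/30 against 30/70: bias = g × (0.7 − 0.3) = 4, 8 or 12 points.

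The false-positive rate is the power of a two-sided 5% t-test against that bias. It has n = 10 per group, 18 degrees of freedom and noncentrality (bias/SD) × √(10/2). For g = 10, full separation and SD 25, the noncentrality is 0.4 × √5 = 0.894 and the rate is 13.5%. The SD of about 25 is given for a single scale. A sum of four scales would have SD √4 × 25 = 50 if they were independent and 4 × 25 = 100 if perfectly correlated, so all three are shown.

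| SD | Split | g = 10 | g = 20 | g = 30 |
|---|---|---|---|---|
| 25 | one regimen per group | 13.5% | 39.5% | 71.8% |
| 25 | 70/30 vs 30/70 | 6.3% | 10.4% | 17.4% |
| 50 | one regimen per group | 7.1% | 13.5% | 24.6% |
| 50 | 70/30 vs 30/70 | 5.3% | 6.3% | 8.0% |
| 100 | one regimen per group | 5.5% | 7.1% | 9.7% |
| 100 | 70/30 vs 30/70 | 5.1% | 5.3% | 5.7% |

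A larger SD lowers the false-positive rate because noise hides the bias. The bias in points is unchanged.

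**Step 4: the Magnitude comparator.** If QID women make up a share P of all TID/QID women and a share p of the Magnitude group, Dosing vs Magnitude shifts by g × (p − P). With P = 0.5 (assumed) and p = 0.7, that is 0.2g, or 2, 4 or 6 points.

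**The case against.** The strongest reply is that current dosing is meant only to separate BID women from TID/QID women, as Table 1 and criterion 3 suggest. I accept that as the better reading. It leaves the division of the TID/QID women with no rule at all.

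Two stronger conclusions are tempting. A reader might infer that TID women go to one group and QID women to the other, which would make strategy and regimen inseparable. The documents do not support this: section d and Table 1 place both regimens in both groups, so the full-separation rows above are an outer limit. A reader might also infer that staff steer women expected to cope towards one schedule. No text says so. Patient preference, site, enrolment order or daily dose would fit the silence equally well.

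Other parts of the defence stand:

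- The contrasts that answer primary question 1 are within woman and are not touched.
- Magnitude vs Frequency is absent from the list in section e and follows only from the general sentence in section d.
- In Dosing vs Magnitude, BID against TID/QID is the exposure, not a confounder. Randomising TID/QID women would not make BID status random.
- Dosing women elect their schedule (Table 1), and women who remain intolerant and want further attempts may choose another strategy (section d). Randomisation cures neither.
- Criterion 3 asks women to accept assignment by current dosing, which is not agreement to be randomised.

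These limit the reach of the problem and of the remedy. None supplies a working rule.

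**Conclusion.** The point holds in limited form. The allocation rule as written is non-random and cannot be carried out for 20 of the 30 planned women. The across-group comparisons are therefore open to confounding by regimen, starting dose, site or selection. That is the most the text supports, since it does not show that confounding will occur.

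The size cannot be derived from the documents. Under the assumed regimen effects of 10 to 30 points and a 70/30 imbalance, the bias is 4 to 12 points. The upper end is 12/30 = 40% of the 30-point difference (25% of 120) that the plan calls clinically meaningful. The false-positive rate then lies between 5.1% and 17.4%, depending on the SD. These figures treat regimen as the only source of bias and hold the SD fixed. Bias from starting dose, site or selection would add to it or offset it.

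**What to change.** Replace the rule in section d with 1:1 block randomisation of TID/QID women to Magnitude or Frequency, stratified by TID vs QID. Amend the wording about current dosing in inclusion criterion 3, and the consent, to match.

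If randomisation is not adopted, label every across-group comparison descriptive and adjust for regimen, starting dose and site. Regimen adjustment applies to Magnitude vs Frequency. In comparisons with the Dosing group, regimen is the exposure, so report the TID/QID mix of the comparator and adjust for starting dose and site only.

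Either way, state in section e that Dosing vs Magnitude is a non-randomised comparison, because BID status is not assigned.

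The cost is a protocol and consent amendment at both sites and a randomisation list for 20 women, with spare entries because section G replaces women who are dropped. No extra procedures are needed and the planned group sizes stay the same.
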